13.1. Adverse event reporting

The main criterion for tolerability is the occurrence of toxicities and adverse events. The severity and causality will be classified according to the NCI CTCAE Version 4. The CTCAE is available for downloading on the internet at <http://evs.nci.nih.gov/ftp1/CTCAE/About.html>. An interactive version can be found at <http://safetyprofiler-ctep.nci.nih.gov/CTC/CTC.aspx>.

An adverse event is defined as any untoward medical occurrence that occurs from the first dose of study medication until 30 days after the final dose, regardless of whether it is considered related to a medication.

Symptoms of the targeted cancer (if applicable) should not be reported as adverse events.

An overdose, accidental or intentional, whether or not it is associated with an AE, of an investigational product should be reported as an SAE.

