13.2. Targeted adverse events

The presence or absence of any of the following adverse events will have to be indicated on each occasion that an Adverse Event Form (Form 41-AE) is completed.

Adverse events should be graded using the NCI CTCAE version 4.0. The following list provides targeted adverse events (ordered by System Organ Class) that should be recorded on the eCRF at any time. Treatments to alleviate these should be recorded on the 41-CCM Form:

Reproductive system and breast disorders:

Vaginal dryness

Dyspareunia

Psychiatric disorders:

Libido decreased

Depression

Anxiety

Insomnia

Renal and urinary disorders:

Urinary incontinence

Vascular disorders:

Hot flashes
Hypertension
Thromboembolic event

Musculoskeletal and connective tissue disorders:

Osteoporosis
Myalgia
Arthralgia

Injury, poisoning and procedural complications:

Fracture

Nervous system disorders:

Stroke
Transient ischemic attacks
Intracranial hemorrhage

Cardiac disorders:

Acute coronary syndrome
Myocardial infarction
Ventricular arrhythmia
Ventricular fibrillation

Gastrointestinal disorders:

Nausea

General disorders and administration site conditions:

Fatigue
Injection site reaction

Immune system disorders:

Allergic reaction

Metabolism and nutrition disorders:

Glucose Intolerance
Hyperglycemia

Investigations:

Aspartate aminotransferase (AST) increased
Alanine aminotransferase (ALT) increased
Blood bilirubin increased
Electrocardiogram QT corrected interval prolonged

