14.1. Case report forms schedule

| | | |
|--|---|---|
| Registration/Randomization | | ALL data should be submitted in iDataFax (iDF) (unless otherwise specified) |
| Informed Consent Form | Consent to participation in clinical trial including consent for biomaterial submission | Obtain before randomization and keep with patient records as documentation (hard copy only). |
| 41-A | Confirmation of Registration Form | Complete in iDF after you or your Randomization Center has randomized the patient in the IBCSG Reg./Rand. System. |
| 41-PRS | Patient-Reported Symptoms | Patient to complete prior to randomization and fax into DataFax after randomization. |
| Baseline | | |
| 41-H | History Form | Complete in iDF within 1 week of randomization. |
| Pathology Report | Pathology Report on diagnostic biopsy | Fax Report to DataFax System within 1 week of randomization. |
| 41-PBx | Pathology Form for diagnostic core biopsy | Complete in iDF within 1 week of randomization. |
| 41-BS | Baseline Symptoms Form | Complete in iDF within 1 week of randomization. |
| 41-CCM | Concomitant Medications Form | Complete in iDF each time a medication is started, amended, or ended, including within 14 days of starting treatment, during treatment, and during follow-up. |
| 41-TEV-B | Baseline Tumor Evaluation Form | Complete in iDF within 1 week of randomization. |
| During trial treatment | | |
| 41-AE | Adverse Events Form | Complete in iDF at the end of each 28 day cycle. |
| 41-TEV | Tumor Evaluation Form | Complete in iDF at the end of cycle 3 and prior to surgery. |
| 41-PRS | Patient-Reported Symptoms | Complete at day 1 of cycle 2 and 4 (i.e. after 4 and 12 weeks), and prior to surgery. |
| 41-CCM | Concomitant Medications Form | Review the original CCM Form at the end of each cycle. Update in iDF any current medications if needed and add new medications taken. |
| 41-PT (Cycle 1) | Protocol Therapy Form (including lab values) | Complete in iDF at the end of cycle 1. |
| 41-PT (Cycles 2-6) | Protocol Therapy Form (including lab values) | Complete in iDF at the end of cycles 2-6. |
| Surgery | | |
| 41-C | Surgery Form | Complete in iDF 30 days after surgery. |
| 41-P | Pathology Form | Complete in iDF 30 days after surgery. |
| Pathology Report | Pathology Report for definitive surgery | Fax report to DataFax System within 30 days after surgery. |
| End of treatment, after surgery | | |
| 41-AE | Adverse Events Form | Complete in iDF 30 days after surgery. |

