 - Partial Response (PR): A 50% or more decrease in total tumor size (i.e. the product of the lesion's maximal diameter (MD) and the corresponding largest perpendicular diameter (LPD) of lesion) which have been measured to determine the effect of the therapy. In addition, there can be no appearance of new lesions or progression of any lesion;
 - Stable Disease (SD): Neither a 50% decrease in total tumor size (i.e. the product of the lesion's two diameters, MD*LPD of lesion) nor a 25% increase in the size of one or more measurable lesions has been determined;
 - Progressive Disease (PD): An increase of at least 25% in total tumor size relative to the smallest size measured during the trial and/or appearance of one or more new lesions.
6. Safety and tolerability: Adverse events (AE) were collected using CTCAE v4.0.
 - a. Each targeted AE will be classified according to the maximum grade of the event while on trial treatment (grade 0,1,2,3,4,5; where 0=no report).
 - b. Other grade 3-5 AEs will be classified according to the maximum grade of any reported other AE.
 7. Patient-reported symptoms (PRS) outcomes (see Section 2.2.6)

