 - Objective response (CR/PR as best overall response) rate was summarized as N (%) with 90% CI, overall and by treatment arm, as well as the absolute percent difference of objective responses between arms were reported with exact binominal 90%CI.
 - Clinical responses at the end of cycle 3 and 6, including complete response (CR), partial response (PR), stable disease (SD) and progressive disease (PD) were descriptively summarized by treatment arms.
- Safety and tolerability

Tolerability was evaluated in each treatment arm separately, using the safety population. For each patient, the targeted AEs recorded over time were summarized for each AE type as the maximum grade reported for that AE (without regard to reported relation to study treatments). The frequencies and percentages of patients experiencing each targeted AE were reported according to maximum grade, separately by treatment arm.. Two-sided 90% exact confidence interval (CI) for the difference in proportion of patients with each type of grade 3 or higher targeted AE between the treatment arms were assessed.

- The maximum grade of all targeted AEs are summarized by treatment arm, and the number and percentage of patients experiencing at least one grade 3 or higher targeted AE will be reported (with CI) according to treatment arm.
- Targeted adverse events (AEs) and other (non-targeted) grade 3 or higher AEs occurring during study were collected using CTCAE v4.0 on the AE Form. The AE Forms were submitted at the end of every cycle (27 days) and 30 days after surgery. All patients submitted AE data during 6 cycles of treatment period when available.
- AEs are reported as maximum grade. The maximum grade consolidates the reports of a given type of AE for a patient over time by taking the maximum

(worst grade) across time (i.e., a patient appears only once for a given type of AE). Patients with reports of multiple AEs of different types are reported multiple times under the relevant AE categories. Maximum grade 0 indicates that the AE type was not reported.

▪ Patient-reported symptoms (PRS) analysis

Longitudinal assessments collected PRS outcome at *baseline* (prior to randomization), at *day 1 of cycle 2 (day 29)*, at *day 1 of cycle 4 (day 85)* of triptorelin or degarelix administration and prior to surgery.

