3.4 PATIENT DEMOGRAPHICS AND BASELINE DISEASE AND PRIOR TREATMENT

Characteristics of the ITT population will be summarized overall and according to treatment assignment. Continuous variables are summarized descriptively (e.g., mean, SD, minimum, maximum, and interquartiles(IQR)). Categorical variables are summarized as N (%); for variables with unavailable (missing, unknown, not done) values, the default approach is to list the number of unknowns as a category but calculate percentages excluding these unknowns from the denominator.

- Stratification factors (as analyzed)
- Patient:
 - Age at randomization
 - BMI at randomization
 - ECOG Performance status at randomization
 - Smoking status/history
 - Oral contraceptive use
 - Centrally assessed baseline E2 levels)
 - Baseline AE/symptoms, comorbidity history
- Pre-treatment Disease characteristics:
 - Tumor size or tumor lesion (via WHO criteria): product of maximum diameter (MD) and largest perpendicular diameter (LPD) of target lesions at baseline), multiple assessments (clinical, mammography, ultrasound)
 - Grade (centrally assess via core biopsy)
 - Histologic type (ductal, lobular, not determinable)
 - ER, PgR status, Allred score, and Her2 status of core biopsy
 - Clinical Nodal status
 - Ki67 label index (%)
 - Baseline CEA, CA15-3: CEA (carcinoembryonic antigen) and CA15-3 (breast cancer associated antigen)
- Prior Treatment (Hform):
 - Type of prior endocrine therapies: SERM, AI and GnRH/LHRH agonist (eligibility exclusions for any endocrine Rx taken within 12 months or oral contraceptive use within 2 months of rando), mainly to confirm not taken it.
- Tables
 - Characteristics, overall ITT population and by treatment assignment

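### The targeted-AE tables take the maximum on-treatment grade without reference to the baseline symptoms collected on Form 41-BS, so conditions present at entry can be counted as events

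*SAP*

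**What the plan says.** **Definition and capture.** Protocol 13.1 defines an adverse event as "any untoward medical occurrence that occurs from the first dose of study medication until 30 days after the final dose". Protocol 13.2 lists the targeted terms, which include hypertension, insomnia, anxiety, depression, fatigue and arthralgia, and sets how they are recorded: "The presence or absence of any of the following adverse events will have to be indicated on each occasion" that Form 41-AE is completed. It does not ask whether the condition is new or has worsened.

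**Analysis.** SAP 2.2.4 states: "Each targeted AE will be classified according to the maximum grade of the event while on trial treatment". SAP 2.2.6 repeats the rule ("the targeted AEs recorded over time were summarized for each AE type as the maximum grade reported for that AE"), applies it "without regard to reported relation to study treatments", and explains the lowest category: "Maximum grade 0 indicates that the AE type was not reported". Protocol 15.2.1 also tabulates worst grade on treatment by arm. Both documents plan 90% confidence intervals for the difference between arms only for targeted events of grade 3 or higher.

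**Baseline data.** The trial schedule in Protocol section 2 has a mandatory pre-randomization row for baseline symptoms. Protocol 14.1 lists the "Baseline Symptoms Form" (41-BS), due within a week of randomization. The only planned use is in SAP 3.4, where "Baseline AE/symptoms, comorbidity history" is one line of the baseline characteristics table.

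**The concern.** Several targeted terms describe conditions that premenopausal women with newly diagnosed breast cancer can have before the first injection. If such a condition persists and is marked present on the AE form, the patient enters the on-treatment table at whatever grade was recorded, even if nothing has changed. Neither document defines a treatment-emergent event, compares on-treatment grade with baseline grade, or plans a shift table for targeted events.

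SAP 2.2.6 evaluates tolerability in each arm separately, and randomization does not protect a within-arm frequency from this kind of inflation. Protocol 15.3 notes that no safety data yet exist for this degarelix regimen with letrozole in this population, so those frequencies are a main safety output of the trial. In the comparison between arms, counting entry conditions in both arms makes a real difference look smaller.

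**Working it through.** The plan states no figure on this point, so there is none to reproduce. The check has a textual part and an illustration.

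**Text.** The rules in SAP 2.2.4, SAP 2.2.6 and Protocol 15.2.1 use only on-treatment reports. Grade 0 means not reported on the AE form; it does not mean no worse than at entry. The baseline table in SAP 3.4 gives totals by arm. It cannot show which on-treatment reports were already present in the same patient, because that needs a patient-level link.

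**Inputs.** 25 patients per arm is the planned number (Protocol 15.1.1, SAP 1.3). The documents give no baseline symptom prevalence and no event rates, so the following are assumptions: b, the share with the symptom at entry, taken as equal in both arms and varied from 10% to 40%; every such symptom persists and is marked; and p, the new-onset rate among the rest, is 20% in one arm and 40% in the other.

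**Effect on the table.** The proportion shown is b + (1 − b)p. The difference shown is (1 − b)(p₂ − p₁). At b = 20%: 0.20 + 0.80 × 0.20 = 36% and 0.20 + 0.80 × 0.40 = 52%.

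| b | Shown, arm with p = 20% | Shown, arm with p = 40% | Difference (points) | Ratio |
|---|---|---|---|---|
| 0% | 20% | 40% | 20 | 2.00 |
| 10% | 28% | 46% | 18 | 1.64 |
| 20% | 36% | 52% | 16 | 1.44 |
| 40% | 52% | 64% | 12 | 1.23 |

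**What treatment-emergent counting recovers.** At b = 20%, new onsets over all patients are 0.80 × 20% = 16% and 0.80 × 40% = 32%. The inflation is gone and the ratio is back to 2.0, but the difference is still 16 points. The 20-point difference returns when the denominator is patients free of the symptom at entry (20% vs 40%), or over all patients if worsening among those who entered with it is as frequent as new onset. The denominator must therefore be stated.

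**Chance imbalance at entry.** The SD of the baseline difference between arms of 25 is √(2b(1 − b)/25): 11.3 points at b = 20%, 13.0 at 30% and 13.9 at 40%. From two independent Binomial(25, b) counts, an imbalance of at least 4 patients (16 points) has probability 21%, 28% and 31% respectively. A patient with the symptom at entry raises the count only if she would not have developed it anyway, so the share carried into the on-treatment table is 1 − p. At p = 20%, 11.3 × 0.8 = 9.0 and 13.9 × 0.8 = 11.1 points. At p = 40%, 11.3 × 0.6 = 6.8 and 13.9 × 0.6 = 8.3 points.

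**Grade 3 or higher.** If 1% to 4% of patients had a targeted condition of that grade at entry (assumed), the same SD formula gives 2.8 to 5.5 points before any carry-over reduction.

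**The case against.** **Sites may not mark unchanged conditions.** A reader might infer that pre-existing conditions are in fact ticked every cycle, contrary to the protocol's definition. The documents do not establish this. Protocol 13.1 dates an adverse event from the first dose and 13.1.3 requires start dates, so a site could properly leave out an unchanged condition. The completion instructions would be in the sample CRFs and the Data Managers' Manual, which are not among the documents reviewed. This stands: conditions can be counted, not that they are. What remains is that the analysis has no rule of its own, and sites may differ.

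**The SAP follows the protocol.** Worst grade on treatment is what Protocol 15.2.1 prespecifies, so the SAP does not depart from it. This stands, and it is a reason not to move the grade 3 or higher intervals onto a different definition.

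**Baseline is partly visible.** SAP 3.4 shows baseline symptoms by arm, and the FACT-ES analysis models scores over time from a baseline assessment for overlapping symptoms such as hot flashes and vaginal dryness. This helps, but it does not cover insomnia, anxiety or hypertension as targeted events, and it does not correct the AE counts.

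**Chance imbalance is not bias.** It is ordinary sampling variation under randomization, which an exact interval already reflects. A treatment-emergent table has its own noise: with b and p each between 20% and 40%, the SD of the arm difference goes from about 13.6–14.1 points to 9.2–13.2 when only new onsets are counted. The argument for the change is what the table means; the gain in precision is modest.

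**Form 41-BS may not carry grades.** The documents give its name and timing only. This stands, and the fix allows for it.

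**Conclusion.** The point holds as an omission with a cheap remedy. Nothing in either document keeps conditions present at entry out of the targeted-AE tables, although baseline symptoms are collected. All-grade, within-arm frequencies are the most exposed. Under the stated assumptions, a 20% new-onset rate would read 28% to 52% as b goes from 10% to 40%, and a 20-point difference between arms would read 18 to 12. These sizes rest on assumed prevalences and on full persistence and reporting; with partial reporting they are smaller.

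Three stronger readings are not supported. There is no systematic advantage to either arm, because allocation is randomized and the same rule applies to both. A baseline imbalance does not pass in full into the on-treatment table, since only about 1 − p of it does. The formal grade 3 or higher comparisons are not shown to be materially affected: pre-existing cases of that grade are probably few in patients with ECOG 0–1 who were screened for serious disease. The endpoint is secondary and descriptive and no decision rule depends on it, so this is an improvement and not a defect that threatens the trial's conclusions.

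**What to change.** Keep the protocol's worst-grade table and its 90% confidence intervals for grade 3 or higher targeted events. Add to SAP 2.2.6:

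1. A treatment-emergent table by arm. A targeted event counts if the term was absent at baseline or if its maximum on-treatment grade is higher than the grade on Form 41-BS. If 41-BS records presence without grade, count new onset only.
2. A shift table of baseline by maximum on-treatment grade for each targeted term, by arm. Its absent-at-baseline row gives the proportion among patients free of the symptom at entry.
3. A statement of the denominator used for each proportion.

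The cost is one merge of Forms 41-BS and 41-AE and the added tables, with no new data collection. First check that 41-BS covers the targeted terms and whether it is graded. The SAP is written largely in the past tense with a September 2017 cutoff, so the addition should be labelled as an added supplementary analysis.

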| PATIENT-REPORTED SYMPTOMS | 
The patient-reported symptoms (PRS) will be assessed using the Functional Assessment of Cancer Therapy Endocrine Subscale (FACT-ES) comprising 18 items (each has score range from 0 to 4) with a possible maximum total score of 72. Functional Assessment of Chronic Illness Therapy (FACIT) guidelines will be used for scoring and interpretation of the FACT-ES total score. Patients will be asked to complete a PRS Form at baseline (prior to randomization), at day 1 of cycle 2, at day 1 of cycle 4, and prior to surgery.
 
The objectives are:
 
 • To assess the differences in PRS score over time between the two treatment arms • To correlate the estradiol (E2) levels and total PRS score measured on day 1 of cycle 2 and day 1 of cycle 4 of triptorelin or degarelix administration • To summarize each of the 18 individual (endocrine symptom) items of the FACT-ES descriptively over time as the proportion of patients with “clinically significant” symptoms (those scoring 3 or 4) |
| STRATIFICATION | 
Stratification will be performed according to:
 
 • Age (in years): less than or equal to 39 versus 40 or more |
| STATISTICAL CONSIDERATIONS | 
To achieve the primary objective, E2 levels will be determined centrally from samples taken at day 1 of the first treatment cycle before the administration of the first dose of degarelix or triptorelin (baseline), and thereafter at 24 and 72 hours, 7 days and 14 days after the first injection, and on day 1 of cycles 2 to 6 before the administration of degarelix or triptorelin.
 
For sample size calculation, we assume that the cumulative percentages of patients in the triptorelin arm achieving optimal ovarian function suppression (defined as E2 ≤ 2.72 pg/mL or ≤ 10 pmol/L) will be 30% within 2 weeks, 60% within 4 weeks and 75% within 8 weeks, and that degarelix will provide more rapid suppression (i.e., 60% within 2 weeks, 95% within 4 weeks and 100% within 8 weeks). Enrollment of 25 patients in each treatment arm will provide at least 90% power to detect a difference in time to optimal ovarian function suppression between the two groups, using a two sample log-rank test with a two-sided significance level of 0.05.
 |

| | |
|----------------------------------|--|

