6.1. Criteria for patient eligibility

- 6.1.1. Female gender
- 6.1.2. Premenopausal status determined locally:
Estradiol (E2) must be above 54 pg/mL (or above 198 pmol/L), measured within 14 days prior to randomization.
- 6.1.3. Age \geq 18 years
- 6.1.4. Performance Status – Eastern Cooperative Oncology Group (ECOG) 0-1 (see chart at end of section*)
- 6.1.5. Histologically confirmed invasive breast cancer:
 - Primary tumor greater than 2 cm diameter, measured by clinical examination and mammography or echography (cT2-4b)
 - Any nodal stage
 - No evidence of metastasis (M0)
- 6.1.6. Primary tumor must have ER and PgR $>50\%$ of the cells
- 6.1.7. Primary tumor must be HER2 negative (by IHC and/or ISH)
- 6.1.8. Hematopoietic status:
 - Absolute neutrophil count $\geq 1.5 \times 10^9/L$
 - Platelet count $\geq 100 \times 10^9/L$
 - Hemoglobin ≥ 9 g/dL
- 6.1.9. Hepatic status:
 - Serum total bilirubin $\leq 1.5 \times$ upper limit of normal (ULN). In the case of known Gilbert's syndrome, a higher serum total bilirubin ($< 2 \times$ ULN) is allowed
 - AST and ALT $\leq 2.5 \times$ ULN
 - Alkaline phosphatase $\leq 2.5 \times$ ULN
- 6.1.10. Renal status: Creatinine $\leq 1.5 \times$ ULN
- 6.1.11. Negative serum pregnancy test, within 2-weeks (preferably 7 days) prior to randomization. Pregnancy test has to be repeated before treatment start if treatment does not start within 15 days of the previous test.
- 6.1.12. The patient must be willing to use effective non-hormonal contraception (barrier method – condoms, diaphragm – also in conjunction with spermicidal jelly, or total abstinence) after the pregnancy test and up to surgery. Oral, injectable, or implant hormonal contraceptives or medicated IUD are not allowed within 2 months prior to randomization and during the trial.
- 6.1.13. Prior fertility treatment is allowed but must have been stopped at least 12 months before randomization

- 6.1.14. The patient has completed the baseline patient-reported symptoms questionnaire
- 6.1.15. Written Informed Consent (IC) must be signed and dated by the patient and the Investigator prior to randomization
- 6.1.16. The patient has been informed of and agrees to data transfer and handling, in accordance with national data protection guidelines
- 6.1.17. The patient accepts blood samples to be taken according to the schedule in section 17.4 for the determination of the primary endpoint

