16.2. PRS Objectives

The primary objective is to assess the differences in patient-reported symptoms (PRS) measurements between the two treatment arms over time. The PRS scores are measured at baseline, day 1 of cycle 2 and cycle 4 of triptorelin or degarelix administration and prior to surgery.

Secondary objectives are:

- To correlate estradiol levels with the total PRS score measured on day 1 of cycle 2 and day 1 of cycle 4 of triptorelin or degarelix administration.
- To summarize each of the 18 individual (endocrine symptom) items of the FACT-ES descriptively over time as the proportion of patients with “clinically significant” symptoms (those scoring 3 or 4).

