16.3. PRS Patient selection

All patients randomized into this trial are required to complete Patient-Reported Symptoms Form 41-PRS. Patients must complete a baseline PRS Form prior to randomization. There will be no patient selection within Participating Centers. The only exceptions are physical impairment that interferes with any assessment.

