16.5. PRS assessment

Patient-reported symptoms will be assessed using the Functional Assessment of Cancer Therapy Endocrine Subscale (FACT-ES). The FACT-ES (42) comprises 18 items, with a maximum possible sum score of 72. Each item or question has response choices ranging from 0 (“not at all”) to 4 (“very much a problem”). FACIT guidelines (www.facit.org) will be used for scoring and interpretation of the FACT-ES total score. To provide clinically useful information regarding treatment side effects, patient responses to each ES question can be labeled as “clinically significant” if they scored 3 or 4 (corresponding to “quite a bit” or “very much” a problem, respectively, on the questionnaire) and as “not clinically

significant” for scores of 0, 1, or 2 (“not at all”, “a little bit”, or “somewhat” a problem, respectively) (34). The questionnaire is completed before any subsequent procedures or treatment and refers to the past 7 days.

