The PRS were assessed using the Functional Assessment of Cancer Therapy Endocrine Subscale (FACT-ES: for endocrine symptom) comprising 19 items (each has score range from 0 to 4) with a possible maximum total score (denoted as ESS) of 76. Functional Assessment of Chronic Illness Therapy (FACIT) guidelines will be used for scoring and interpretation of the FACT-ES total score.

The primary endpoint was FACT-ES total score (or ESS). Note that the FACT-ES items are negatively framed, thus scores were reversed for analysis so that high scores equate to a good quality of life (QOL) [Lesley et al]

In order to better describe the specific type of QOL measures, as exploratory analysis, four subscales/groups of FACT-ES were also summarized, namely,

- Vasomotor symptoms (VS, score 0-12): hot flashes, cold sweats, night sweat (note: sleeping difficult was an item not collected in our dataset)
- Neuropsychological symptoms (NS, score 0-16): light-headed/dizzy, headache, mood swings, feeling irritable (lack of energy, nervous were not collected in our study)
- GI symptoms (GIS, score 0-16): Vomiting, Gained weight, Diarrhea, bloated feeling (nausea no data)
- Gynecologic symptoms (GYNS, score 0-28): vaginal discharge, vaginal irritation, vaginal bleeding, vaginal dryness, discomfort intercourse, lost interest in sex, breast tenderness

To provide clinically useful information regarding treatment side effects, patient responses to each ES question are labeled as “clinically significant” if they scored 3 or 4 (corresponding to “quite a bit” or “very much” a problem, respectively, on the questionnaire) and as “not clinically significant” for scores of 0, 1, or 2 (“not at all”, “a little bit”, or “somewhat” a problem, respectively). The questionnaire is completed before any subsequent procedures or treatment and refers to the past 7 days.

All patients who received at least one dose of study treatment and with at least one FACT-ES assessment were included in the analysis (PRS population=ITT population).

The differences in FACT-ES scores (ESS) measurements between the two treatment arms over time were assessed using a mixed-effect model (SAS proc mixed, note a change from GEE model stated in the protocol, due to the small sample size and for simplicity). The ESS

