scores as well as the 4 subscales and individual FACT-ES items were modeled as a function of time and treatment arm to investigate the time pattern of FACT-ES scores and differences controlling for the stratification factor of age (dichotomized ≤ 39 vs $40+$ years). The covariance structure used *autoregressive* (type =AR(1) assuming between observations on the same patient are not equal but decrease toward zero with increasing lag). All available data were included in the model.

This model described the effects of two neoadjuvant treatments (degarelix+letrozole or triptorelin+letrozole) on FACT-ES for the observation period. The analysis will be exploratory, given the limited sample size (maximum 25 patients per treatment arm). The power of the repeated measure test is likely to be low except if treatment differences are substantial.

Means scores at each timepoint for each treatment arm, and for the difference between the treatment arms, were estimated from the models and reported with 90% CIs.

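### The PRS mixed model does not use the baseline score to sharpen the post-baseline arm differences. This loses precision but causes no bias. Separately, the FACT-ES item count needs reconciling.

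*SAP*

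**What the plan says.** **Model.** SAP 2.2.6 replaces the protocol's GEE with a mixed model. The ESS, four subscales and individual items are "modeled as a function of time and treatment arm to investigate the time pattern of FACT-ES scores and differences controlling for the stratification factor", namely age, with AR(1) covariance and all available data. Arm means and arm differences are reported at each timepoint with 90% CIs. Protocol 16.6.1 also controls for age only. Neither document names baseline ESS as a covariate, a change score, or an equal-baseline constraint. The arm-by-visit term is not named either.

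**Baseline form.** Protocol 6.1 makes it an eligibility criterion: "The patient has completed the baseline patient-reported symptoms questionnaire". Protocol 16.3 requires the forms of all randomized patients and adds: "The only exceptions are physical impairment that interferes with any assessment". The baseline value should therefore be nearly complete.

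**Item count.** SAP 2.2.6 describes the FACT-ES as "comprising 19 items (each has score range from 0 to 4) with a possible maximum total score (denoted as ESS) of 76". The protocol summary (section 1) has it "comprising 18 items (each has score range from 0 to 4) with a possible maximum total score of 72", section 16.5 says it "comprises 18 items, with a maximum possible sum score of 72", and section 16.2 refers to "each of the 18 individual (endocrine symptom) items of the FACT-ES". SAP 1.4.1 reports no amendment.

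**The concern.** A patient's symptom score before treatment usually predicts her score afterwards. A model that ignores this leaves explainable variation in the arm difference. With at most 25 patients per arm, and low power conceded in both documents, that precision is worth having. Protocol 16.6.1 hypothesizes a more rapid onset of symptoms on degarelix, and day 1 of cycle 2 is the first form after baseline, so an early difference would appear there first.

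The item count is a smaller matter. It fixes the range of the score that the SAP names as the PRS primary endpoint, and it would enter any proration for missing items.

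**Working it through.** **Inputs.** From the documents: 25 per arm; visits at baseline, cycle 2, cycle 4 and pre-surgery; AR(1) covariance; 90% CIs. Assumed, because the documents give no PRS correlation: adjacent-visit correlation ρ of 0.3, 0.5 or 0.7, equal variances and complete data. Standard errors are in SD units. There is no PRS sample-size or power figure to reproduce.

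**1. SAP model, with separate arm means at each visit.** An unconstrained baseline mean in each arm absorbs the baseline data, so the estimate at a visit is the plain difference in means:

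SE = √(2/25) = 0.283, and the 90% CI half-width is 1.645 × 0.283 = 0.465.

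**2. Using baseline.** If the arms share one baseline mean, the visit difference is corrected by the chance baseline difference. The SE is multiplied by √(1 − c²), where c is the baseline-to-visit correlation:

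- c = 0.3: 0.283 × √0.91 = 0.270, or 5% smaller
- c = 0.5: 0.283 × √0.75 = 0.245, or 13% smaller
- c = 0.7: 0.283 × √0.51 = 0.202, or 29% smaller

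**3. Where the gain falls.** Under AR(1), c is ρ, ρ² and ρ³ at the three visits. SE reductions:

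| ρ | Cycle 2 | Cycle 4 | Pre-surgery |
|---|---|---|---|
| 0.3 | 5% | 0% | 0% |
| 0.5 | 13% | 3% | 1% |
| 0.7 | 29% | 13% | 6% |

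If the correlation does not decay, the cycle 2 column applies at all three visits.

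**4. Check by simulation** (25 per arm, AR(1) true and known, age in the model, 4,000 runs). Ratios of SE to the SAP model at cycle 2 / cycle 4 / pre-surgery:

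| ρ | Equal-baseline model | Baseline as covariate |
|---|---|---|
| 0.3 | 0.95 / 1.00 / 1.00 | 0.97 / 1.00 / 1.01 |
| 0.5 | 0.86 / 0.97 / 0.99 | 0.87 / 0.99 / 1.01 |
| 0.7 | 0.71 / 0.87 / 0.94 | 0.72 / 0.89 / 0.95 |

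The covariate version pays for its slope by a factor of about √(1 + 1/45) = 1.011. It breaks even at c = √(1/46) = 0.15.

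If the true correlation is constant at 0.5 but AR(1) is kept, the equal-baseline ratios are 0.85 / 0.89 / 0.94. The later visits then miss part of the gain (√0.75 = 0.87), which is the reason for an unstructured covariance.

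**5. In terms of power.** For a true difference of 0.5 SD, the chance that the 90% CI excludes zero is 54% unadjusted (noncentral t, 47 df). At cycle 2 it is 56%, 64% or 78% with baseline as covariate (46 df, slope cost included).

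**6. Item count.** The SAP's total is consistent in itself: 19 × 4 = 76. Its four groups list 3 + 4 + 4 + 7 = 18 items with maxima 12 + 16 + 16 + 28 = 72, which matches the protocol's 18 × 4 = 72. Adding the item in "bloated feeling (nausea no data" would give 19, but the same list marks three other items as not collected (sleeping difficulty, lack of energy, nervousness), so this does not settle the count. Reversing a sum from 76 instead of 72 adds 4 points in both arms and leaves the difference unchanged; reversing item by item does not involve the count. Only proration to 19 from 18 collected items, which the documents do not describe, would rescale arm differences, by 19/18, or 5.6%.

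**The case against.** The SAP carries out the adjustment that the protocol specified, age only, in an analysis that both documents call exploratory. Keeping baseline as a modelled visit fits the stated objective, which counts baseline among the measurements. The gain rests on an assumed correlation, and treatment starts between baseline and cycle 2, so a high value across that interval cannot be taken for granted. Much of SAP 2.2.6 is in the past tense, so a new model would not be pre-specified. All of this stands. It sets the priority and the form of the fix, but does not remove the loss.

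Several stronger readings are tempting, and the documents do not support them:

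- *That the arm differences are biased.* Baseline is measured before randomization, so any baseline imbalance is due to chance.
- *That the loss is confined to cycle 2.* This holds only if AR(1) is true.
- *That the model has one arm effect common to all visits.* Under AR(1), such a model would put weight 1/(4 − 2ρ), that is 29%, 33% or 38%, on the pre-treatment difference and dilute any effect. The term is not named, but reporting a difference at each timepoint implies separate effects.
- *That the SAP's adjustment of a Cox model for baseline E2 sets a precedent.* That model supplements an age-stratified primary test.
- *That the SAP's 19 items strictly contradict its own list.* The four groups are not said to exhaust the scale. The conflict with the protocol remains.

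**Conclusion.** The point holds as a loss of precision. On the reading that arm means are free at each visit, baseline ESS contributes nothing to the post-baseline differences. Using it would reduce the SE at a visit by about 5%, 13% or 29% at an assumed correlation with baseline of 0.3, 0.5 or 0.7, before estimation costs. At about 0.3 or lower the gain is small or nil. How it spreads over the visits depends on whether the correlation decays. No trial decision rests on PRS, so this is a low-priority improvement from a value already collected.

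The item count is a documentation conflict. A reader might infer that reported scores are wrong, but nothing in the documents shows an incorrect score or arm difference.

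**What to change.** 1. For the ESS and the four subscales, keep all four visits as responses, name the arm-by-visit term, constrain the arm means to be equal at baseline, and keep the age stratum. Use unstructured covariance with Kenward-Roger degrees of freedom.
2. If that does not converge, model the three post-baseline visits with baseline score and baseline-by-visit as covariates, and a covariance that allows a separate variance at each visit. This drops patients with only a baseline form, whom the SAP 2.1 PRS population includes, and any without a baseline form; the constrained model keeps both.
3. If the SAP 2.2.6 model has already been run, report the new fit beside it as a labelled additional analysis.
4. Check Form 41-PRS and reconcile the item count across the two documents before stating the ESS range or applying any proration.

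The cost is a few lines of code and a wording check. The unstructured covariance has 10 parameters for four visits, against 2 for AR(1), in about 50 patients; hence the fallback.
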